#### Study Summary

**Study Title:** A Mixed Methods Observational Study to Determine the Sources and Impact of Indoor Air

Pollution in Patients with Chronic Respiratory Disease.

Internal ref. no. and short title: RG\_21-096; IndoorAirVG

Study Design: Mixed methods study with 3 parts

Part 1: qualitative research exploring patient perceptions and sources of indoor air pollution/poor indoor air quality.

Part 2: questionnaire study to independent group of patients regarding findings of part 1.

Part 3: observational cohort study, distributing indoor air monitors to patients, and gathering symptom and indoor air quality data over a period of 2 weeks.

Study Participants: Subjects with any pre-existing respiratory disease, as determined by their clinician

Planned Size of recruitment target: Part 1: 20-30 patients, Part 2: ≥100 patients, Part 3: 60 patients. There may be overlap between parts 1 or 2 and 3, such that a patient may participate in any one or all three parts of the study.

Follow up duration: Parts 1 and 2: nil. Part 3: 2 weeks

Planned Study Period: 1 year

Research Question/Aim(s): To Determine the Sources and Impact of Indoor Air Pollution in Patients with

Respiratory Disease.

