#### 2. Rationale

We have systematically reviewed published work on indoor air quality and its health effects, and found an evidence gap relating to respiratory patients. As such a focus onto this group is required.

Indoor Air Quality VG is a mixed methods study recruiting respiratory patients from within the NHS, and collecting research data remotely/virtually (parts 1 and 2) or in person (part 3). Patients will be managed for their respiratory disease according to their local procedures and policies with no interference from the study team. Patients will give informed consent to participate to each part of the study independently, and will be able to participate in either part 1, 2, and part 3, or one part alone. The key outputs are expected to be (i) A prioritised list of areas in which indoor air quality or indoor/outdoor interfaces (IOIs) contribute to perceptions of respiratory and general health (ii) A list of health outcomes which would be most important to assess in studies of psychological and/or technological interventions identified by other groups working within the parent grant. We anticipate challenges related to the diversity of patients' lives and environments, their understanding of what is possible in short-medium term interventional studies, such as those which may stem from our initial work, and the potential for off target deleterious effects - for example avoiding poor air quality could result in lower physical activity if patients stay in one area, and this is known to be harmful to health[10, 11]. For this reason, we have chosen a mixed method design where we can fully explore views in an initial qualitative package, before refining our inquiry in a questionnaire to a larger group of patients, independent of those participating in the qualitative work. We will then test the potential for indoor air to influence day to day symptoms by way of a short-term monitoring study.

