#### 4. Study design and methods of data collection and data analysis

#### Part 1: Understanding VGs perceptions on indoor AQ

This part of the project will recruit 20-30 people, which is likely to be the amount required to reach data saturation. All will give informed consent.

Focus groups of up to 6 people, or individual interviews, according to patient preference, will be conducted using the topic guide, which will inquire about sources and impacts of indoor air pollutants, and about IOIs. The interviews will be conducted by a trained researcher, recorded and transcribed verbatim. Where possible interactions will take place virtually, to ensure a degree of robustness to any future Covid related disruptions, and to provide greater convenience to participants. Interactions will be recorded using the technology available on the virtual meeting platform Zoom, both recording and transcription will occur on a University owned computer. Where a participant feels they cannot use a virtual medium or telephone, face to face will be offered as an alternative. Should face to face be required this will occur either on the University campus or in the patient's home. If a home visit is required the University lone worker policy will be adhered to. Data will be stored in an anonymised manner. Qualitative analysis using the Framework method [12], which is a systematic approach well suited to interdisciplinary health research and to working with clinical and lay collaborators.

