#### Part 2: Understanding VGs perceptions on indoor AQ and interventions to improve AQ

This part of the study will recruit a minimum of 100 patients, however if more wish to participate this will be allowed, since costs and logistics of the study will not rise unduly with more participants. As this is an exploratory part of the study no formal power calculations are possible or required at this stage. Consent will be taken remotely only, and the questionnaire distributed as a link to an electronic survey provided by Microsoft Forms. Participants can also request a paper equivalent, which will be sent by post thereafter. The questionnaire will take approximately five minutes to complete for each participant.

Data from the thematic analysis will be used to design a questionnaire inquiring about sources and impacts of indoor AQ, especially at IOIs, and the impact of each on respiratory symptoms and overall health. This will verify the findings of part 1, and will go further by also inquiring about usability and acceptability of interventions possible to improve each potential source. Data will be stored in an anonymised manner electronically. Each question will use a binary yes/no response, or a numerical response (e.g. Likert scale) and data will be analysed using simple descriptive statistics only. Responses from those with asthma and those with COPD will also be subgrouped and analysed separately.

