#### Inclusion criteria

Either COPD or asthma, as defined by their referring/usual care clinician in the medical record. The same inclusion criteria apply across all 3 parts of the study. Participants in this study need to be over the age of 16 and able to give informed consent.

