#### Exclusion criteria

Patients unwilling or unable to participate in the study; again, this applies across all 3 parts of the study.

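### The protocol calls the Part 2 survey group independent of Part 1 but allows a patient into all three parts and sets no bar, so part of the verification could come from the people who supplied the themes

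*Protocol*

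**What the plan says.** **Independence.** The Study Summary defines Part 2 as a "questionnaire study to independent group of patients regarding findings of part 1". Section 2 (Rationale) makes this part of the reason for the mixed-methods design: the questionnaire goes to a larger group, "independent of those participating in the qualitative work".

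**Purpose.** Section 4, Part 2, builds the questionnaire from the Part 1 thematic analysis and says: "This will verify the findings of part 1". It adds a second aim, the usability and acceptability of possible interventions.

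**Overlap.** Under the planned recruitment size, the Study Summary allows overlap "such that a patient may participate in any one or all three parts of the study". The Rationale says that patients "will be able to participate in either part 1, 2, and part 3, or one part alone".

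**Eligibility.** "The same inclusion criteria apply across all 3 parts of the study". The only exclusion reads: "Patients unwilling or unable to participate in the study; again, this applies across all 3 parts of the study". The Consent section asks for separate consent for each part and mentions no check on earlier participation.

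**Size and handling of data.** For Part 1, "This part of the project will recruit 20-30 people". Part 2 takes at least 100, with no upper limit. Part 2 answers are stored anonymised and summarised descriptively.

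**The concern.** Part 2 can verify Part 1 only to the extent that its respondents are not the people whose accounts produced the themes. Someone who raised a source of poor indoor air in an interview is likely to endorse it again when asked in a survey. That answer repeats Part 1 and adds no confirmation.

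The protocol recognises this by claiming independence twice, but nothing in it secures that independence and one sentence gives it away. What is at stake is the reported level of agreement with each theme. That agreement feeds the first key output named in the Rationale, a prioritised list of areas where indoor air contributes to perceived health.

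The inflation would not be visible in a table of percentages. Since the stored data are anonymised and no marker of Part 1 participation is described, the overlapping answers may not be removable later.

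**Working it through.** **1. Do the statements conflict?**

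- The overlap sentence in the Study Summary opens by speaking of Part 1 or Part 2 overlapping with Part 3. Taken alone, that would keep Parts 1 and 2 apart.
- It ends with "such that a patient may participate in any one or all three parts of the study". Anyone in all three parts is in both Part 1 and Part 2. That ending cannot stand beside the independence claim in the same summary.
- The Rationale's wording, "will be able to participate in either part 1, 2, and part 3, or one part alone", can mean Parts 1, 2 and 3 together, or one of Parts 1 and 2 plus Part 3. It does not settle the matter.
- The Inclusion criteria, Exclusion criteria and Consent sections supply no bar.

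The conflict is therefore clear in the Study Summary, and the Rationale leaves it unresolved.

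**2. How large can the overlap be?**

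The protocol states no figure for overlap, so there is none to reproduce. The inputs are 20-30 people in Part 1 and at least 100 in Part 2 (section 4). The largest possible share is s = n(Part 1) / n(Part 2).

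| Part 2 respondents | 20 in Part 1 | 30 in Part 1 |
|---|---|---|
| 100 (the minimum) | 20/100 = 20% | 30/100 = 30% |
| 200 (illustration) | 20/200 = 10% | 30/200 = 15% |

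These are ceilings. They are reached only if every Part 1 participant also answers the survey.

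**3. What bias follows?**

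If new patients endorse a theme with probability p and Part 1 patients with probability p + d, the survey reports (1 - s)p + s(p + d) = p + s × d. The bias is s × d. The protocol gives no endorsement rates, so d is an assumption.

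| Overlap s | d = 20 points | d = 40 points |
|---|---|---|
| 10% | 0.10 × 20 = 2 | 0.10 × 40 = 4 |
| 20% | 0.20 × 20 = 4 | 0.20 × 40 = 8 |
| 30% | 0.30 × 20 = 6 | 0.30 × 40 = 12 |

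A 40-point gap is, for example, 90% among Part 1 patients against 50% among new patients. The survey would then report 54%, 58% or 62% in place of 50%.

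**4. How does this compare with sampling error?**

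The 95% margin at p = 0.5 is 1.96 × √(0.25/n).

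- n = 100: 9.8 points
- n = 80 (20 of 100 set aside): 11.0 points
- n = 70 (30 of 100 set aside): 11.7 points

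Of the six bias figures above, only the largest (12 points) exceeds the margin at 100 respondents.

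**The case against.** The strongest defence is that this is loose drafting. Independence is stated plainly twice. The overlap sentence begins with Part 3 overlap only, and the Rationale's sentence can be read the same way. Clear permission then rests on one phrase. This is fair as to intent, and it is why the Rationale sentence is called ambiguous here and is not counted as a second permission. But the phrase is there, and no eligibility rule corrects it. Nor can the matter be left to an analysis plan, because it concerns who may enter Part 2, which the protocol itself fixes.

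Several stronger readings are tempting, and the document does not support them.

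- *That all parts draw on the same patients.* The recruitment section lists routes without assigning them to parts, but the section on roles and responsibilities names the patient advisory group as a route for Part 2.
- *That overlapping respondents could never be removed.* Consent is documented separately for each part, so the team could know at enrolment who joined both. The data protection section speaks of de-identified data, a weaker term. Linking a particular survey answer may be difficult, but the text does not show that it is impossible.
- *That the prioritised list is distorted.* A ranking changes only if the inflation differs between themes. That is possible but not shown. Objective 1 also intends interviews and questionnaires to contribute together.
- *That 30% overlap is to be expected.* It requires all 30 Part 1 patients to respond and Part 2 to stop at exactly 100.

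It also stands that Part 2 is exploratory and descriptive. No test or power calculation depends on the independence of the two groups. The circularity argument does not reach the intervention questions either, which go beyond Part 1.

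**Conclusion.** The concern holds as an inconsistency with a possible, partial effect. The protocol claims an independent Part 2 sample, permits overlap in the Study Summary and has no criterion to prevent it. The contradiction itself is certain on the text. The bias is conditional on overlap actually occurring and on an endorsement gap that is assumed, since the protocol gives no rates. Within the illustrated range it runs from 2 to 12 points, and in most of that range it is smaller than the sampling margin at 100 respondents.

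A reader might infer that the verification is circular as designed. The figures do not support that: even at the ceiling, 70-80 of 100 respondents would be new patients. The protocol should still be corrected before Part 2 opens, because the correction is cheap then and may not be possible once anonymised answers are stored.

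**What to change.** Preferred change:

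- Reword the overlap sentences in the Study Summary and the Rationale so that a patient may combine Part 1 or Part 2 with Part 3, but not Part 1 with Part 2.
- Add to the Exclusion criteria that Part 1 participants are not eligible for Part 2. Part 3 overlap stays as it is.

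The cost is wording, plus at most 30 potential respondents lost from a survey with no upper limit. Parts 1 and 2 would together need at least 120-130 different people (20 + 100 to 30 + 100). The answers of Part 1 patients on intervention usability and acceptability would also be lost.

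Alternative, if those answers are wanted:

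- Let Part 1 participants into Part 2 and correct the independence statements to say so.
- Add one yes/no item to the Part 2 form asking whether the respondent took part in a Part 1 interview or focus group.
- Leave those who answer yes out of the analysis that verifies Part 1, and keep them for the intervention items.

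The cost is one survey item. If 20-30 of 100 respondents are set aside, the margin for the verification results is about 11.0-11.7 points, against 9.8 with all 100. Recruiting the same number of additional new respondents restores it.

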### Funding and Support in Kind

FUNDER(S)	FINANCIAL AND NON FINANCIAL SUPPORT GIVEN
NERC, Natural Environment Research Council, [name]	Overall value of award: £504644
United Kingdom. Funder award number NE/V002414/1	

#### Role of Study Sponsor and Funder

The Sponsor is the Institution assuming overall responsibility for the initiation and management of the study and is not the main funder. The funder provides the budget for the work but does not have responsibility for its conduct. They will monitor progress with the project overall, of which this study is one work package, and will be recognised on publications arising from the work, but do not control decision to publish.

# Roles and responsibilities of study management committees/groups and individuals

There are no study specific committees, however the University of Birmingham Respiratory Patient Advisory Group have been consulted about the overall aims of the project and content of the topic guide, as well as the structure of the patient information sheets. They will also be approached to aid recruitment to part 2 of the study, and for dissemination of results about the project. The wider grant within this project sits also engages the public and other stakeholders through a series of events that inquire about indoor air quality.

### Study Flow Chart

### Study Protocol

#### I. Background

Air pollution causes 29,000 pre-mature deaths and costs the economy £20 billion per year in the UK alone. The majority of these impacts are associated with Vulnerable Groups (VGs), who are most strongly affected by air pollution with up to ca. 12 life years lost for the individual. People with pre-existing medical conditions, in particular those where the lung is affected, are of particular concern in terms of long-term health, societal and economic impacts. Despite this, most of the efforts in air quality improvement focusses on the general population and outdoor exposure. This potentially promotes inequalities and leads to major gaps in understanding exposure to key air pollutants (particularly PM1, ultrafine particles and VOCs), health risks and economic consequences, and the key challenges and mitigation options for these Vulnerable Groups. The CleanAir4VG project grant to which this specific project contributes aims to build a self-sustaining and interdisciplinary network of academics, stakeholders and industry capable to deliver co-designed research and innovation to develop robust solutions that reduce the impact of pollution on VGs; and to cross-link to UK and international expertise to establish research gaps, effective behaviour and technology intervention opportunities and catalyse future cross-disciplinary research capability.

This patient centred work package aims to understand the sources of poor air quality (AQ) indoors for people with respiratory diseases such as asthma and chronic obstructive pulmonary disease (COPD). A systematic review of 56 studies (3 from the UK) has shown an association between short term exposure to pollutants (NO2, PM2.5, CO and PM10) and acute exacerbations (AE) of respiratory disease, in particular AECOPD [1]. The attributable fraction for hospital admissions for COPD was 9.7% for the 6 pollutants considered [1], thus of the 140,000 admissions/year for COPD[2], outdoor pollutants account for around 13,594 admissions/year. Hence we anticipate that hospital admissions will be a key outcome for VGs, however long term decline of lung function in adults has also been identified in our prior research as a potential outcome of interest [3]. However, day to day symptoms may be a more feasible outcome for interventional studies arising from the parent grant, being shorter and thus less expensive in nature. They are also relevant to the types of pollutant likely to be present indoors, such as small particulates (E.g. PM2.5). Air purifiers may reduce PM2.5 by up to 57%[4], and have been associated with improvement in peak expiratory flow rate (PEFR) variability in asthma[5] as well as reductions in exhaled nitric oxide (FeNO)[4], a measure of eosinophilic inflammation linked to asthma control. Short term change in PM2.5 has potential to improve symptoms from COPD[6] and has been shown to reduce arterial stiffness[7], which relates to COPD severity[8] and risk of death[9]. We will therefore explore association of indoor pollutants with symptoms in one part of our study.

#### 2. Rationale

We have systematically reviewed published work on indoor air quality and its health effects, and found an evidence gap relating to respiratory patients. As such a focus onto this group is required.

Indoor Air Quality VG is a mixed methods study recruiting respiratory patients from within the NHS, and collecting research data remotely/virtually (parts 1 and 2) or in person (part 3). Patients will be managed for their respiratory disease according to their local procedures and policies with no interference from the study team. Patients will give informed consent to participate to each part of the study independently, and will be able to participate in either part 1, 2, and part 3, or one part alone. The key outputs are expected to be (i) A prioritised list of areas in which indoor air quality or indoor/outdoor interfaces (IOIs) contribute to perceptions of respiratory and general health (ii) A list of health outcomes which would be most important to assess in studies of psychological and/or technological interventions identified by other groups working within the parent grant. We anticipate challenges related to the diversity of patients' lives and environments, their understanding of what is possible in short-medium term interventional studies, such as those which may stem from our initial work, and the potential for off target deleterious effects - for example avoiding poor air quality could result in lower physical activity if patients stay in one area, and this is known to be harmful to health[10, 11]. For this reason, we have chosen a mixed method design where we can fully explore views in an initial qualitative package, before refining our inquiry in a questionnaire to a larger group of patients, independent of those participating in the qualitative work. We will then test the potential for indoor air to influence day to day symptoms by way of a short-term monitoring study.

#### 3. Research question/aims

The study objectives are:

- 1. To identify the environments and/or locations that VGs considered to be important in their exposure to poor air quality indoors. This will be achieved by a combination of qualitative research and questionnaires
- 2. To identify symptom-based health outcomes driven by air quality based on symptoms and indoor air quality monitoring. This will be achieved using a daily symptom diary and an air quality monitor, used over a period of minimum 2 weeks, maximum 6 weeks.

#### 4. Study design and methods of data collection and data analysis

#### Part 1: Understanding VGs perceptions on indoor AQ

This part of the project will recruit 20-30 people, which is likely to be the amount required to reach data saturation. All will give informed consent.

Focus groups of up to 6 people, or individual interviews, according to patient preference, will be conducted using the topic guide, which will inquire about sources and impacts of indoor air pollutants, and about IOIs. The interviews will be conducted by a trained researcher, recorded and transcribed verbatim. Where possible interactions will take place virtually, to ensure a degree of robustness to any future Covid related disruptions, and to provide greater convenience to participants. Interactions will be recorded using the technology available on the virtual meeting platform Zoom, both recording and transcription will occur on a University owned computer. Where a participant feels they cannot use a virtual medium or telephone, face to face will be offered as an alternative. Should face to face be required this will occur either on the University campus or in the patient's home. If a home visit is required the University lone worker policy will be adhered to. Data will be stored in an anonymised manner. Qualitative analysis using the Framework method [12], which is a systematic approach well suited to interdisciplinary health research and to working with clinical and lay collaborators.

#### Part 2: Understanding VGs perceptions on indoor AQ and interventions to improve AQ

This part of the study will recruit a minimum of 100 patients, however if more wish to participate this will be allowed, since costs and logistics of the study will not rise unduly with more participants. As this is an exploratory part of the study no formal power calculations are possible or required at this stage. Consent will be taken remotely only, and the questionnaire distributed as a link to an electronic survey provided by Microsoft Forms. Participants can also request a paper equivalent, which will be sent by post thereafter. The questionnaire will take approximately five minutes to complete for each participant.

Data from the thematic analysis will be used to design a questionnaire inquiring about sources and impacts of indoor AQ, especially at IOIs, and the impact of each on respiratory symptoms and overall health. This will verify the findings of part 1, and will go further by also inquiring about usability and acceptability of interventions possible to improve each potential source. Data will be stored in an anonymised manner electronically. Each question will use a binary yes/no response, or a numerical response (e.g. Likert scale) and data will be analysed using simple descriptive statistics only. Responses from those with asthma and those with COPD will also be subgrouped and analysed separately.

